7.4.4.1 Corneal endothelial cell density

Specular microscopy allows a clear view of live endothelial cells without altering their function or morphology. In turn, a surface area count can be performed to determine if there is an alteration in the shape or size of the endothelial cells, parameters that must be taken into account to determine the functional capacity of the corneal endothelium. CEC density decreases over time, due to diseases and intraocular surgical procedures. Analysis of CEC density will be performed using a specular microscope

(the make and model of the equipment must be specified). The density in cells/mm² will be recorded in the eCRF. The area and strategy used in the scrutiny visit must be the same as the final visit.

Management as AE: This value, by itself, will not be considered an AE regardless of the changes; the AE will correspond in each case to a clinical corneal decompensation when so judged by the PI.

7.4.4.2 Intraocular pressure

Tonometry is the objective measure of IOP, based primarily on the force required to flatten the cornea, or the degree of corneal depression produced by a fixed force. Goldman tonometry is based on the Imbert-Fick principle. [34]

Tonometry will be performed after instillation of topical anesthetic with fluorescein and the use of a cobalt blue filter (after assessing surface staining). Two readings will be taken, and the average will be recorded in the clinical record. The average will be recorded in the eCRF.

Management as AE: IOP peaks ≥ 30 mmHg should be reported as AE.

7.4.4.3 Adverse events

As described in section 8.2, an adverse event is defined as Any adverse medical occurrence in a subject to whom an investigational product is administered, regardless of causal attribution.

The management of adverse events will be carried out in accordance with the provisions of Section 8. Evaluation and management of adverse events and incidents.

Any adverse events that study subjects experience will be reported by the PI in the corresponding section of the eCRF and also in the clinical record.

For an adequate assessment of adverse events, in addition to the targeted questioning, a Comprehensive Ophthalmologic Evaluation must be performed at each visit. This evaluation consists of: ophthalmologic examination of the eyelids and adnexa; anterior and posterior segments, which are performed during a routine ophthalmologic examination, procedures not specifically included in the study variables. The posterior pole evaluation may be performed with direct or indirect ophthalmoscopy, with or without pharmacological mydriasis, at the discretion of the PI. The fundus will be assessed for abnormalities that could alter the study results. IOP will be measured during this evaluation, using the PI's chosen instrument, and should be measured after the stain evaluation. The results of the evaluation will be recorded in the clinical record. Only those findings that the Principal Investigator considers to be adverse events will be reported in the eCRF.

Adverse events (including incidents, adverse events) that may occur with the use of PRO-149 or Healon® EndoCoat medical devices are: ocular inflammation (iritis, hypopyon, endophthalmitis), increased intraocular pressure, corneal edema, secondary glaucoma, corneal decompensation, cystoid macular edema, blurred vision, burning, ocular pain, ocular irritation, breakage of intraocular lens haptics, foreign body on ocular surface.

7.4.4.4 Changes in corneal thickness

Pachymetry, the measurement of central corneal thickness, will be performed simultaneously with the CEC density measurement using a specular microscope (the brand and model of the equipment used must be specified). It will be recorded in the eCRF.

Management as AE: This value, by itself, will not be considered an AE regardless of the changes; the AE will correspond, in each case, to clinical corneal decompensation when so judged by the PI.

7.4.4.5 Cellularity and flare in the anterior chamber

In the presence of intraocular inflammation, increased permeability of the non-pigmented layer of the ciliary epithelium, the posterior iris epithelium, and the iris vascular endothelium results in the accumulation of cells and proteins (visible to the examiner as flare) in the anterior chamber. Using a 0.2mm X 0.2mm light beam directed obliquely into the anterior chamber with a forward tilt of the light source (slit lamp tower), the degree of flare and cellularity will be determined according to the Uveitis Nomenclature Standardization Working Group. [35] The degree of agreement will be reported in the eCRF according to the given grade (See **Table 4** and **Table 5**).

Table 4. Scale for anterior chamber cellularity

Degree	Number of cells
0	None
½ +	1-5
1 +	6-15
2 +	16-25
3 +	26-60
4 +	More than 60

Visible in a 0.2mm x 0.2mm field

Table 5. Flare scale

Degree	Number of cells
0	There is no flare
1 +	Mild
2 +	Moderate (iris and lens clearly visible)
3 +	Marked (iris and lens slightly blurred)
4 +	More than 60 (fibrin)

Management as AE: Reported values ≥ 3 for cellularity or flare should be reported as AE.

7.4.4.6 Best Corrected Visual Acuity

Visual acuity (VA) is a test of visual function. Spatial visual acuity is the ability to distinguish separate elements of an object and identify them as a whole. It is quantified as the minimum angle of separation (located at the nodal point of the eye) between two objects that allows them to be perceived as separate objects.

Snellen notation is described as the distance at which the test is performed divided by the distance at which the letter is vertically equivalent to 5 minutes of arc. Thus, at 6 meters a letter 6/6 (20/20) is equivalent to 5 minutes of arc, a letter 6/12 (20/40) is equivalent to 10 minutes, and a letter 6/60 (20/200) is equivalent to 50 minutes. The Snellen fraction can also be expressed as a decimal (i.e., 20/20 = 1 and 20/40 = 0.5).[34]

VA will be assessed at baseline, without refractive correction, using the Snellen chart. This chart will be placed in a location with adequate natural or artificial lighting and at a distance of 3 m from the subject being assessed. Visual acuity will be measured in the study eye, asking the subject to keep both eyes open and using an occluder to cover the contralateral eye. The subject will read aloud the lines indicated by the

evaluator. The line with the smallest letters visible will be recorded by the evaluator as a fraction of the OD VA in the clinical record.

The subject's best refractive correction will then be performed, and the examination will be repeated using the obtained refraction. This result will be reported as best-corrected visual acuity, recorded as a fraction and decimal in both the clinical record and the eCRF.

Management as AE: This value, by itself, will not be considered an AE regardless of the changes; the AE will correspond, in each case, to clinical corneal decompensation when so judged by the PI.

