8.2 Definition of adverse event, incident, adverse incident and adverse effect

According to the International Conference on Harmonization (ICH), an adverse event (AE) is any unfavorable medical occurrence in a clinical research subject administered a pharmaceutical product, regardless of causal attribution. [38, 39, 40]

Therefore, an AE may be any of the following: any unfavorable, unintended disease, symptom, or sign (including an abnormal laboratory finding) that is temporally related to the use of a medical product, whether or not considered to be related to that product; any new disease or exacerbation of an existing disease (worsening of the nature, frequency, or severity of a known condition); relapse of an intermittent medical condition (e.g., headache) not present at baseline; any deterioration in a laboratory value or other clinical test (e.g., electrocardiogram [ECG], X-ray) that is related to the symptoms or that results in a change in study or concomitant treatment or discontinuation of study drug. [38, 39, 40]

As defined in the previous paragraph, an adverse event is defined as any event that occurs during treatment with a drug or device. However, the definition can also apply to any undesirable event that occurs during a clinical trial, including behavioral disturbances. [40]

According to NOM-240-SSA1-2012, an incident is any event related to the use of a medical device; while an adverse incident is any proven event related to the use of a medical device that has conclusive evidence of the causal relationship between the incident and the medical device, and that could be caused by a malfunction or alteration of the characteristics of the medical device and that could cause death or serious deterioration of the health of the user. An adverse incident will not be considered an incident derived from abnormal use or a use different from that recommended by the holder of the sanitary registration of the medical device or its legal representative in Mexico. [37]

According to NOM-012-SSA3-2012, an adverse effect is the set of uncalculated and unexpected signs and symptoms that occur in a research subject, as a consequence of the application of experimental maneuvers planned in a protocol or research project for health in human beings and that potentially represent a risk to their health. [41]

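### The AE rules for BCVA, corneal thickness and cell density name only corneal decompensation; this conflicts with 7.4.4.3 and 8.2, so recording of some events depends on the section applied

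*Combined protocol and SAP*

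**What the plan says.** **Variable-specific rules.** Section 7.4.4.6 says of BCVA that a change in the value alone, whatever its size, is not an AE, and that "the AE will correspond, in each case, to clinical corneal decompensation when so judged by the PI". Section 7.4.4.4 on corneal thickness opens the same way ("This value, by itself, will not be considered an AE regardless of the changes") and names the same diagnosis. Section 7.4.4.1 on cell density ends almost identically: "the AE will correspond in each case to a clinical corneal decompensation when so judged by the PI".

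**General rules.** Section 7.4.4.3 sets a broad duty: "Any adverse events that study subjects experience will be reported by the PI in the corresponding section of the eCRF". To support it, "a Comprehensive Ophthalmologic Evaluation must be performed at each visit", covering anterior and posterior segments, together with targeted questioning. Its list of possible AEs includes "corneal edema, secondary glaucoma, corneal decompensation, cystoid macular edema, blurred vision". It also limits what reaches the eCRF to the findings that the investigator regards as AEs. Section 8.2 covers any unfavorable disease, symptom or sign, and also "any deterioration in a laboratory value or other clinical test" where this is related to symptoms or leads to a change in, or discontinuation of, treatment. Section 8.3 asks for every undesirable manifestation, related or not.

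**Where it counts.** AE incidence is a secondary outcome (7.4.2). The trial is open-label except for the statistical analysis (7.3).

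**The concern.** It is defensible not to treat a bare measurement as an AE. The difficulty is the second half of the sentence, which gives a single corneal diagnosis as the AE in every case. That suits a corneal measurement better than it suits BCVA. Acuity can also fall through macular edema, inflammation or a lens problem, and 7.4.4.3 itself lists events of these kinds. The BCVA wording matches the corneal-thickness wording and may have been carried over from it, though that is an inference.

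For the corneal measures, 7.4.4.3 and the risk list in 2.2.2 both treat corneal edema and corneal decompensation as different events. Sections 7.4.4.1 and 7.4.4.4 name only the second.

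At stake is the consistency of AE recording in a trial whose objective is safety. If a site turns to the variable-specific paragraph when deciding whether a finding is an AE, it may reach a different answer from a site that turns to 7.4.4.3 or 8.2.

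**Working it through.** The plan gives no figure to reproduce for this point. The check is to run typical postoperative findings through both sets of rules.

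| Finding | 7.4.4.1, 7.4.4.4 or 7.4.4.6, read literally | 7.4.4.3, 8.2 and 8.3 |
|---|---|---|
| BCVA fall, clear cornea, cystoid macular edema found | Not the AE named | AE: listed by name in 7.4.4.3 |
| BCVA fall, clear cornea, patient complains of blurred vision | Not the AE named | AE: blurred vision is listed; the 8.2 clinical-test clause is also met through the symptom |
| Corneal edema that the investigator does not call decompensation | Not the AE named | AE: listed separately from decompensation |
| BCVA fall or corneal thickening with no symptom, no diagnosis and no change of treatment | Not an AE | No clear trigger: the clinical-test clause is not met, and whether the value alone is a sign is left to judgement |

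1. In the first three rows the general route captures the event and the specific rule, read literally, does not. That is the contradiction. No section states which prevails.
2. In the fourth row neither route gives a firm trigger. Other variables differ here: IOP of 30 mmHg or more (7.4.4.2) and cellularity or flare of grade 3 or more (7.4.4.5) must be reported as AEs.
3. Timing matters for the third row. Under 1.3, specular microscopy and pachymetry are done only at screening and Day 29. Edema present on Day 1 or Day 8 that clears before Day 29 would not show in either measure, so the AE form is its most direct record.

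**Reference-trial figures (2.2.2).** AEs of IOP at or above 30 mmHg: 10.5% × 200 = 21 and 7.5% × 200 = 15, so 21 + 15 = 36. Then 36/39 = 92.3%, which agrees with the stated 92%. The other three were cystoid macular edema, haptic damage requiring lens exchange, and a surface foreign body. None is corneal decompensation, but 7.4.4.3 lists cystoid macular edema, haptic breakage and surface foreign body, so all three would be reportable here. The figures therefore do not measure an under-count.

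**Sensitivity of the outcome.** With 18 subjects per arm (10.2.1), one subject recorded differently moves that arm's incidence by 1/18 = 5.6 percentage points. This shows how coarse the outcome is. It does not estimate how often the conflict would arise.

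**The case against.** The strongest reply is that the three rules decide only when a number, taken alone, becomes an AE, and do not restrict what else may be reported. A site bound by 7.4.4.6 is equally bound by 7.4.4.3, which points to Section 8 and requires questioning and an examination of both segments. The device risks listed in 2.2.2 all reappear by name in 7.4.4.3. BCVA and corneal thickness are analyzed as secondary outcomes and cell density as a primary one, so the measurements are kept. The safety criterion in 10.1.2 uses only the primary variables, so AE counts do not drive it. Finally, investigator judgement in an open-label trial affects AE reporting generally, not only these three variables.

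Most of this stands. A reader might infer that visual loss from other causes, and edema short of decompensation, drop out of the AE outcome. The documents do not support that, because the general route remains open. A reader might also infer a bias towards finding no difference. The documents do not support that either: an unblinded investigator could err in either direction.

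The reply does not remove the conflict in wording. The sentence goes beyond exempting a bare value by saying what the AE is in each case, and the general route is itself filtered by what the investigator considers an AE.

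**Conclusion.** The concern holds as a contradiction between stated rules. The BCVA rule is wrong as written, and the two corneal rules do not agree with the separate listing of corneal edema in 7.4.4.3. A BCVA fall, or corneal edema short of decompensation, can be recorded as an AE or not depending on which section the unblinded investigator applies.

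The size and direction of any effect on AE incidence cannot be worked out from the documents. The conclusion assumes that some sites would read the variable-specific sentence literally; if every site treats 7.4.4.3 and 8.2 as overriding, the listed events are recorded and only the fourth row of the table stays open. The wording conflict itself is certain. Severity: minor.

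**What to change.** Reconcile the sections.

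- In 7.4.4.6, replace the reference to corneal decompensation with wording such as: *Any AE associated with a fall in BCVA is recorded under the diagnosis that explains it, or as reduced vision if unexplained, whenever it meets the definition in 8.2.*
- In 7.4.4.1, 7.4.4.4 and 7.4.4.6, add: *This rule does not limit reporting under 7.4.4.3 and 8.2, including corneal edema that does not amount to decompensation.*
- Carry the same instruction into the eCRF guidance.

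No numeric threshold is proposed and no measurement is added. Investigator judgement remains, but all sites would apply one definition. The cost is a protocol and eCRF wording change, and possibly a slightly higher AE count in both arms.

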7.4.4.7 Transsurgical evaluation

During the surgical procedure, the surgeon will assess the clinical behavior of the PI. Immediately after completing the procedure, he or she will answer the questionnaire "Evaluation of OVD performance", appendix 15.1. The ability of the OVD to maintain the AC formed during continuous circular capsulorhexis (CCC) and IOL implantation, retention during phacoemulsification, ease of use (including blister removal, syringe assembly, ease of injection), ergonomics, facilitation of CCC performance, transparency during surgery, and ease of removal will be evaluated. They will be graded on a 5-point scale: 0 = very poor; 1 = poor; 2 = acceptable; 3 = good; 4 = very good. The results will be recorded in the eCRF.

Management as AE: Not applicable. The results of this questionnaire should not be considered AE.

7.5 Program of visits and activities of the study

7.5.1 Description of activities per visit

The procedures are listed in the order in which they are suggested, attempting to maintain consistency in the assessments and, as far as possible, from the least invasive to the most invasive.

7.5.1.1 Scrutiny Visit

Signature of the ICF: refers to the signing of the written informed consent document. Without informed consent, none of the study procedures can be performed.

Medical record: refers to the technical, clinical, and legal document that chronologically records the subject's health conditions, medical procedures, and other procedures performed on the subject. It includes anthropometric measurements, anamnesis, a comprehensive ophthalmological examination that allows determining the patient's eligibility, i.e., evaluation of both eyes and ocular adnexa, slit-lamp examination of the ocular surface and anterior segment, and fundoscopy. If the subject is taken from the study center's established population base, the existing medical record may be used; only one update is required.

Somatometry: refers to the measurement of the research subject's weight and height, expressed in kg and cm, respectively. It will be performed with calibrated instruments of the center's choice.

Concomitant Medication Assessment: Refers to the PI questioning the subject about medication use.

Vital signs: refers to taking heart rate, respiratory rate, systemic blood pressure and temperature.

AVMC: See 7.4.4.6

Ophthalmological evaluation: See 7.4.4.3

Ocular tonometry: See 7.4.4.2*

Gonioscopy: Refers to the evaluation of the AC angle. After applying a drop of 0.5% tetracaine ophthalmic solution, the 60° lateral mirror of the goniolens is used to evaluate the iridocorneal angle, which is graded according to the Shaffer classification.

Assessment of pharmacological mydriasis: After checking the AC angle, apply one drop of 5% Phenylephrine/0.8% Tropicamide every 5 minutes, on three occasions. Five minutes after the last application, the pupillary diameter will be measured using a slit lamp. This measurement will be recorded in the eCRF.

Specular microscopy: See 7.4.4.1

Corneal pachymetry: See 7.4.4.4

Eligibility criteria: Refers to the PI's review, which verifies that the subject can be included in the study if they meet all the inclusion criteria and do not meet the exclusion criteria. See 5.1

IOL calculation and anterior chamber measurement: Once the relevant eligibility criteria have been met, the IOL calculation will be performed. This involves biometric measurements (keratometry, anterior chamber depth, and axial length) and their integration into the PI selection formula to determine the power, expressed in diopters, of the IOL to be implanted. This will be performed using the Zeiss IOL Master device (the model must be specified).

Preoperative cardiology evaluation request: This refers to the delivery to the research subject of the requests for laboratory tests (blood pressure, serum calcium and PT/TPT, INR), ECG, and subsequent preoperative cardiology evaluation. The subject must arrive at the scheduled time and date for the tests and evaluation.

AE Assessment: See 7.4.4.3

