7.5.1.6 Final Visit

Vital signs: See 7.5.1.1

Evaluation of concomitant medications: See 7.5.1.1

AVMC: See 7.4.4.6

Ophthalmological evaluation: See 7.4.4.3

Ocular tonometry: See 7.4.4.2

Specular microscopy: See 7.4.4.1

Corneal pachymetry: See 7.4.4.4

AE Assessment: See 7.4.4.3

Return of concomitant treatment: refers to the return of the Sophixin DX® Ofteno bottle by the subject to the research center.

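### The protocol does not ensure that endothelial cell density and corneal thickness are measured under the same eye conditions at baseline and at the final visit

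*Combined protocol and SAP*

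**What the plan says.** Section 7.5.1 explains how to read the visit lists: "The procedures are listed in the order in which they are suggested, attempting to maintain consistency in the assessments". It adds a second aim, that gentler procedures should precede more invasive ones where this can be done. The order is therefore a suggestion with two stated aims.

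For the screening (scrutiny) visit, section 7.5.1.1 lists visual acuity, the ophthalmological evaluation, tonometry, gonioscopy, the mydriasis assessment, specular microscopy and pachymetry, followed by the eligibility review and the IOL calculation. Three of the steps ahead of specular microscopy involve drops or corneal contact:

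- Tonometry, defined in section 7.4.4.2: "Tonometry will be performed after instillation of topical anesthetic with fluorescein and the use of a cobalt blue filter".
- Gonioscopy: "After applying a drop of 0.5% tetracaine ophthalmic solution, the 60° lateral mirror of the goniolens is used to evaluate the iridocorneal angle".
- The mydriasis assessment: "apply one drop of 5% Phenylephrine/0.8% Tropicamide every 5 minutes, on three occasions".

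For the final visit, section 7.5.1.6 lists visual acuity, the ophthalmological evaluation, tonometry, specular microscopy and then "Corneal pachymetry: See 7.4.4.4". No gonioscopy or mydriasis step appears there, and the schedule in section 1.3 ticks both of these once only, at screening.

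Section 7.4.4.1 asks for the same area and strategy in specular microscopy at the two visits. Section 7.4.4.4 has pachymetry done together with the cell-density reading on the same instrument.

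**The concern.** Change in endothelial cell density is a primary outcome and change in corneal thickness a secondary one. Section 1.3 and Table 3 schedule each reading twice, once at screening and once at the final visit. The baseline is thus half of every change score, and no other reading can correct it.

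If the eye is prepared differently on the two occasions, any effect of that preparation becomes part of the measured change. Section 10.1.2 plans repeated-measures tests within each group, and such a test cannot separate a preparation effect from the effect of surgery. The baseline cell density also decides eligibility, through the exclusion below 1500 cells/mm² in section 5.1.2, so that decision rests on a reading listed after contact and dilation.

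**Working it through.** The main check is a comparison of the two lists. The plan has no figure to reproduce.

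| Listed step, in order | Screening (7.5.1.1) | Final visit (7.5.1.6) |
|---|---|---|
| Ophthalmological evaluation (dilation optional, 7.4.4.3) | listed | listed |
| Tonometry: anesthetic, fluorescein, applanation | listed | listed |
| Gonioscopy: tetracaine, goniolens | listed | not listed |
| Mydriasis assessment: three instillations | listed | not listed |
| Specular microscopy, then pachymetry | after all of these | after tonometry |

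1. **Count.** Three defined drop or contact steps precede the corneal readings at screening and one precedes them at the final visit. Discretionary dilation is left out of this count because it may occur at either visit.
2. **Stated aims.** The two lists do not match, so the order does not serve consistency. At screening a contact lens examination and dilation come ahead of specular microscopy and pachymetry, so for these readings the order does not run from less to more invasive either.
3. **Possible remedy elsewhere.** Section 7.4.4.1 covers area and strategy but not prior drops, contact or order. Section 7.4.4.4 ties pachymetry to the same session, so both readings share the mismatch. No other section requires matched preparation.
4. **Between-arm effect.** Suppose preparation shifts every baseline by s. Each observed change is then the true change minus s. With mean true changes D1 and D2 in the two arms, the contrast is (D1 − s) − (D2 − s) = D1 − D2, so a common shift drops out.
5. **Within-group effect, illustration only.** Let b be the absolute size of the shift divided by the SD of the within-eye change. If there is no true change, the two-sided 5% paired t statistic follows a noncentral t distribution with n − 1 degrees of freedom and noncentrality b√n, apart from its sign. The chance of a significant result is the area beyond ± the usual critical value. The n values come from the protocol: 18 per arm planned (10.2.1) and 14 per arm required (10.1.4). The b values are assumptions.

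| Eyes per arm | Assumed b | b√n | False-positive rate |
|---|---|---|---|
| 18 | 0.25 | 0.25 × 4.243 = 1.06 | about 17% |
| 18 | 0.5 | 0.5 × 4.243 = 2.12 | about 52% |
| 14 | 0.25 | 0.25 × 3.742 = 0.94 | about 14% |
| 14 | 0.5 | 0.5 × 3.742 = 1.87 | about 41% |

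With b = 0 the rate is the nominal 5%. The paired t-test follows the rule for normally distributed continuous variables in section 10.1.2. Table 3 names the McNemar test for corneal thickness, so the thickness test is itself unsettled. For cell density a real fall is expected: sections 2.2.1 and 10.2.2 cite falls of 4.7% and 6.97% with 3% hyaluronate. There the practical consequence would be a fall reported as too large or too small rather than a pure false positive.

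**The case against.** The strongest reply is that the trial's conclusion is protected. Section 10.1.2 bases the safety decision on a comparison with the comparator. The product is assigned at the surgery visit (7.5.1.3), after baseline, and both arms follow the same screening list. A common shift therefore cancels, as step 4 shows. This stands. Extra noise between arms would need an effect that varies from eye to eye, and nothing in the documents establishes or sizes one.

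A reader might infer more: that the two readings are in fact taken under different conditions, that the baseline cornea is thickened or its images degraded, or that the 52% is an expected error rate. The documents support none of these.

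- The order is only suggested, so a center may already take the readings first.
- Section 7.4.4.3 lets the investigator dilate during the ophthalmological evaluation, listed ahead of specular microscopy at both visits, so dilation may also precede the final readings.
- No section says that a goniolens or dilating drops alter thickness or cell counts, or in which direction.
- The 52% belongs to the larger of two assumed shifts and to the number of eyes before losses.

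The screening entry for tonometry also carries an asterisk with no note in the text available for this review. An ordering note may have been lost and should be looked for in the source file.

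A reader might also extend the point to the IOL Master readings: "This involves biometric measurements (keratometry, anterior chamber depth, and axial length"). These are taken at screening only, so there is no final value to mismatch.

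What survives is that the protocol leaves matching to chance, and that a center following its suggested order would not achieve it.

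**Conclusion.** The point holds as a gap in standardization. The suggested screening order puts the corneal readings after three drop or contact steps, and the final-visit order puts them after one. This runs against the protocol's own aim, and no other rule closes the gap. The exposure is mainly in the within-group tests of change for cell density and thickness, and in the baseline cell density used for eligibility. The between-arm comparison that drives the safety decision is not affected by a shift common to both arms.

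The size of any effect is unknown. The 14% to 52% range in the illustration depends wholly on an assumed constant shift of 0.25 to 0.5 SD, no true change, and a paired t-test. It shows how sensitive the test would be and does not predict what will happen. The case for acting rests on the change being cheap, not on a demonstrated bias.

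**What to change.** In sections 7.5.1.1 and 7.5.1.6, list specular microscopy and pachymetry before any eye drop or contact procedure: tonometry, gonioscopy, and any dilation, including the optional dilation within the ophthalmological evaluation. Use the same order at both visits and state that for these two readings it is required, not suggested.

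No procedure, visit or staff is added. The cost is a protocol amendment, with the committee review and COFEPRIS authorization described in section 11.2, and slightly less flexibility for the center.

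Moving biometry forward as well is a separate, optional choice that concerns screening values only, such as the anterior chamber depth criterion of at least 2.8 mm. It would require rewording section 7.5.1.1, which places the IOL calculation after the relevant eligibility criteria are met. Some eyes would then have biometry and later be excluded for mydriasis below 6 mm.
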